(2) the preliminary efficacy of the Cubii elliptical for increasing activity (primary outcome), physical function, and quality of life, and decreasing physical and psychological symptom (e.g., pain, fatigue, depression) severity in people with MS.

2. Study Design & Methods

To achieve the study aims, we will conduct a prospective observational study that combines self-reported measures and the use of the Cubii exercise unit.

Participation in this study will involve (1) presenting to the UW Medicine Multiple Sclerosis Center (“MS Center”) to complete “baseline” assessments (T1; see section X.X) and receive their Cubii exercise unit; (2) self-directed use of the Cubii exercise unit at home for 8 weeks; and (3) returning to the MS Center to complete a walking test and an assessment (T2).

Study coordinators will maintain a relationship with participants to ensure adherence to the study protocol. This may include contact participants (according to their preferred method) at the midpoint of the self-directed home exercise period to troubleshoot any issues that may have arisen.

Participants will be compensated \$100 for full completion of the study (\$40 for participating at T1 and \$60 after completing the assessments at T2).

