3.2. Study Procedures and Materials

Pre-baseline visits tasks Participants will first complete validated self-report questionnaires (demographics, MS disease-related variables (e.g., pain, fatigue, falls), activity, exercise, quality of life, and biopsychosocial symptom variables).

In-person baseline visit

At the baseline visit (T1), participants will come to the MS Center for a 60-minute visit during which they will take a six-minute walking test, and engage with staff for a brief orientation to the Cubii and its phone app.

Eight-week at-home period

Participants will use the Cubii at home for two months. Participants will use the unit as they choose and maintain a log regarding their device use.

In-person post-treatment visit

Participants will return to the UW MS Center at nine weeks and complete the same validated self-report questionnaires at baseline and provide additional data regarding the feasibility, usability, and satisfaction with the use of the Cubii.

Table 2. Study Activities

Primary Outcomes	Domain	Study Activity	Baseline (week 1)	Weeks 2-8	Week 9
		Demographics	X		X
		Medical/Surgical History/Disease variables	X		
		Anticipated experience/use/satisfaction	X		
		Patient Global Impression of Change (PGIC)	X		X
Additional covariates	Satisfaction with social roles	PROMIS Satisfaction with Participation in Social Roles Short Form 8a	X		X
	Self-efficacy	University of Washington Self-Efficacy Scale short form	X		X
	Resilience	UW Resilience Scale 8-item short form v1.0	X		X
	Comorbidities	Comorbidity Questionnaire	X		X

	Physical Activity Readiness scale	PAR-Q+	X		X
Preliminary efficacy	Physical activity	Godin Leisure Time Exercise Questionnaire	X		X
	Physical function	PROMIS Short Form v2.0 - Physical Function 20a	X		X
	Quality of life	MSQOL54- Quality of Life Subscale	X		X
	Pain intensity	PROMIS Pain Intensity Short Form 3a	X		X
	Pain interference	PROMIS Pain Interference Scale (Short Form 8b, V1.0)	X		X
	Fatigue interference	PROMIS SF v1.0 - Fatigue- Multiple Sclerosis 8a	X		X
	Depression	PROMIS Short Form v1.0 Depression 8a	X		X
	Anxiety	PROMIS Short Form v1.0 - Anxiety 8a	X		X
	Ambulatory function	CogDetect walking tests	X		X
	Fatigue intensity	Brief Fatigue Inventory (BFI)	X		X
		Measure of falls	X		X
		Spacitcty	X		X

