3.4.1. Self-Report Measures

The participants will complete online self-report surveys via REDCap. Study staff will register participants in REDCap and provide a participant-specific URL to access the surveys. The survey battery will take approximately 20 minutes and study staff will be available to assist as needed. See above table for measures and participant demographics and clinical characteristics: demographic questions (age, sex, gender, race, ethnicity, education, income, marital status,

employment status & healthcare coverage), clinical survey (e.g., time since diagnosis, MS subtype, brief medical and psychiatric history, and other clinical characteristics), and treatment survey (e.g., medications and therapies).

Ambulatory measures

Motor Function: We will administer a 4-m backward walking test, evaluation of gait speed (4 meter walk test), and gait endurance (2-minute walk test).

Backward gait speed: Backward walking is used to assess balance and fall risk. Participants walk backwards a short distance at their usual pace, completing one practice and two-timed trials. Scores are recorded as time in seconds required to walk 4 meters on each of two trials, with the better trial used for scoring. The test time is ~3 minutes.

Gait speed: The 4-meter walking test measures locomotion. Participants walk a short distance at their usual pace, completing one practice and two-timed trials. Scores are recorded as time in seconds required to walk 4 meters on each of two trials, with the better trial used for scoring. The test time is ~3 minutes.

Gait endurance (2-minute walk test): This test assesses the ability to sustain effort that requires conjoint work capacities from cardiopulmonary function, biomechanical, and neuromuscular function. The test time is ~4 minutes.

4. Data Management: Storage and Sharing

We will use REDCap to collect and store study data and participant identifiers. We will (1) assign each participant an ID number in REDCap to maintain confidentiality and (2) use this ID number to code/label study data. The link between the study data and a participant's identity will only exist in REDCap, to which only research staff members have access.

We will label any paper forms only with the ID number and keep them in a locked cabinet separate from any identifying information and will scan and upload them to REDCap as a source document.

We will track protocol deviations and adverse events in REDCap.

5. Data Analysis/Statistical Methods

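### The primary activity outcome is not measured during the eight weeks of use; a midpoint Godin sent by the existing survey link would show it, with little gain in precision for the week-9 change

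*Combined protocol and SAP*

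**What the plan says.** Section 1 gives as the second aim to evaluate "the preliminary efficacy of the Cubii elliptical for increasing activity (primary outcome), physical function, and quality of life". Section 5.2 again names activity as the primary outcome and plans a test of within-person change. It names no test, significance level or missing-data method.

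The only physical-activity row in Table 2 (Section 3.2) is the "Godin Leisure Time Exercise Questionnaire", marked at Baseline (week 1) and Week 9. The Weeks 2-8 column is empty for every row. The text of Section 3.2 agrees: "Participants will return to the UW MS Center at nine weeks and complete the same validated self-report questionnaires at baseline".

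The one data source named for the home period is a log: "Participants will use the unit as they choose and maintain a log regarding their device use".

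Two things that could support a midpoint measurement already exist:

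- Section 2 says of staff contact: "This may include contact participants (according to their preferred method) at the midpoint of the self-directed home exercise period to troubleshoot any issues". This is optional, and no data collection is attached to it.
- Section 3.4.1 says that staff will "provide a participant-specific URL to access the surveys", so the questionnaires already run online.

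Section 5.1 sets N = 20 as a pilot size, gives no effect size, SD or power, and says that the study is underpowered for definitive conclusions. Section 9 asks staff to record why a participant left, but does not say how the missing outcome is handled.

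**The concern.** Participants choose how much to use the unit, so activity could rise early and fade, build slowly, or not change. One value after the use period cannot separate these courses. The log helps with part of this, because it can show whether Cubii use rose or fell. It cannot show whether that use added to a participant's other exercise or replaced it, and total activity is the outcome.

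The second issue is missed T2 visits. With one value before and one after, and no missing-data method, a simple paired comparison drops anyone without a week-9 Godin. In a group of 20, a few such losses matter.

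Both bear on the plan's stated purpose of informing a larger trial. That trial would need to know when to assess activity and how strongly repeated Godin scores correlate. Two time points give one correlation and no course over time.

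**Working it through.** There is no figure of the plan to reproduce, because N = 20 has no power inputs.

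**Inputs.** From the documents: n = 20, one group, Godin at baseline and week 9. Assumed, because the documents give none: equal SD at each time; correlation r between baseline and each later value (r = 0.5 unless stated); correlation q between midpoint and week 9; a paired t test at two-sided 0.05; 0, 2 or 4 of 20 missing week 9, all of whom answered at midpoint. Standard errors are in units of the Godin SD.

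**1. Current design.** SE of the change = √[2(1−r)/n] = √(1/20) = 0.2236. The change detectable with 80% power is 0.66 SD of the change score.

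**2. Baseline-to-week-9 change, with the midpoint in the model.** Let k be the number with a week-9 value and R² the share of week-9 variance explained by the earlier values. Under maximum likelihood with a free mean at each time:

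Var = (1−R²)/k + (R² + 1 − 2r)/n

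With k = n, R² cancels and Var = 2(1−r)/n, the same as in step 1. With complete data the midpoint adds nothing to this estimate.

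With k = 16:

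- No midpoint: R² = r² = 0.25. Var = 0.75/16 + 0.25/20 = 0.05938, SE 0.2437.
- Midpoint, q = 0.5: R² = 0.333. Var = 0.667/16 + 0.333/20 = 0.05833, SE 0.2415.
- Midpoint, q = 0.8: R² = (0.25 + 0.64 − 0.40)/0.75 = 0.653. Var = 0.347/16 + 0.653/20 = 0.05433, SE 0.2331.

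| Missing week 9 | Completers only | Model, no midpoint | With midpoint, q = 0.5 | q = 0.7 | q = 0.8 |
|---|---|---|---|---|---|
| 0 | 0.2236 | 0.2236 | 0.2236 | 0.2236 | 0.2236 |
| 2 | 0.2357 | 0.2327 | 0.2317 | 0.2295 | 0.2279 |
| 4 | 0.2500 | 0.2437 | 0.2415 | 0.2366 | 0.2331 |

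With 4 missing, the midpoint lowers the SE by about 1% to 4% (0.2415/0.2437 = 0.99; 0.2331/0.2437 = 0.96). Recovering two of those four week-9 values by the survey link would take the SE from 0.2437 to 0.2327 without any midpoint, about the same as the best midpoint case.

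**3. Average change over the use period** (mean of midpoint and week 9, minus baseline). Here r₁₂, r₁₃ and r₂₃ are the correlations of baseline with midpoint, baseline with week 9, and midpoint with week 9.

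Var = [1 + (1 + r₂₃)/2 − r₁₂ − r₁₃]/n, against 2(1 − r₁₃)/n for the pre-post change

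| Assumed pattern | Variance ratio | SE ratio |
|---|---|---|
| All equal: 1.5(1−r) / 2(1−r) | 0.75 | 0.866 |
| Decaying with time, adjacent 0.3 | 0.692 | 0.832 |
| Decaying with time, adjacent 0.8 | 0.639 | 0.799 |
| Baseline with later 0.5, later pair 0.6 | 0.80 | 0.894 |
| Baseline with later 0.5, later pair 0.9 | 0.95 | 0.975 |

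The SE falls 13% under equal correlations, and by 2.5% to 20% across the other patterns.

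**4. When averaging loses power.** Let f be the midpoint effect as a fraction of the week-9 effect. Under equal correlations the standardised effect is multiplied by [(1+f)/2]/√0.75. Break-even is f = 2√0.75 − 1 = 0.73. For a week-9 effect of 0.5 SD of change, power is 56% with the pre-post change. With the average it is 69% if f = 1 and 45% if f = 0.5. With r = 0.5 and a later pair at 0.8, break-even rises to 2√0.9 − 1 = 0.90.

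**The case against.** The case for leaving the schedule alone is reasonable. This is a 20-person pilot whose first aim is feasibility, usability and satisfaction. It says itself that it is underpowered, and a pre-post design is legitimate for that purpose. The log already covers the home period to some degree. The midpoint contact is optional, so a Godin from everyone needs a scheduled step and reminders. More time points do not replace the missing comparison group. All of this stands, and it makes the change an inexpensive improvement rather than the repair of an error.

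A reader might infer two stronger things that the documents do not support.

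- **That a midpoint Godin would cut the error of the primary result by about 13%, lowering the detectable change from 0.66 to 0.57 SD of change.** That holds only if the target becomes the period average, the correlations are equal and the midpoint effect is already as large as the week-9 effect. The schedule in Table 2 yields the baseline-to-week-9 change, for which the gain with complete data is zero. If activity builds gradually, which self-directed use allows, averaging can lower power.
- **That anyone who misses T2 would then have a post-use value.** Only participants still taking part who answer at midpoint would have one, and it would be a value during use, not at week 9. Larger savings, such as an SE of about 0.80 of the completers-only SE with 4 missing, require one common effect at both times.

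**Conclusion.** The point holds in a limited form. The primary activity outcome is not measured while the device is in use, and the log does not fill that gap. A midpoint Godin would show activity during use and give some protection to the estimate for participants who answer it and then miss T2. It would also supply the correlations that a larger trial needs.

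The gain in precision is not the reason to do it. For the week-9 change it is nil with complete data and about 1% to 4% of the SE with 4 of 20 missing. For the period average it is about 13% under equal correlations and 2.5% to 20% otherwise.

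These sizes rest on assumed correlations, equal variances and assumed missing counts. They also treat the correlations as known; in 20 people they must be estimated, so the small gains could be smaller still. The protection against missed visits assumes that missing week-9 values are explained by the earlier scores.

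**What to change.** 1. In Table 2, mark the Godin at the midpoint (about week 4-5). Send it to all participants by the existing REDCap link as a scheduled step with reminders, separate from the optional troubleshooting contact in Section 2.
2. In Section 3.2, state that the week-9 Godin may be completed by the same link when the T2 visit is missed. This addresses missed visits more directly than the midpoint does.
3. In Section 5.2, name the baseline-to-week-9 change in Godin as primary. Estimate it with a repeated-measures model on baseline, midpoint and week 9, with a separate mean at each time, so that participants with a midpoint but no week-9 value are kept. State the significance level.
4. Report the average change over the use period as secondary. It should not become primary, because it loses power if the midpoint effect is below about 73% of the week-9 effect.

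Cost: one short online questionnaire and a few minutes per participant, one REDCap schedule entry, some staff time for reminders, and a few sentences in Sections 3.2 and 5.2. No extra visit is needed.

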3.3. Data Collection Technology

We will collect survey data via a secure REDCap website. REDCap is an open-source, secure, HIPAA-compliant web-based platform designed to support data capture for research studies. Vanderbilt University designed it to protect patient privacy and confidentiality while assisting investigators in clinical research. It provides an interface for data entry and validation, auditing features for tracking data manipulation, the ability to import data from external sources, calculated data fields, branching logic, and the capability to export data to many statistical packages. System and application-level security include SSL encryption of internet traffic (https pages), hosting in a secure data center with nightly backup, fine-grained control over user rights, detailed audit trails, record locking, and de-identification features for data export.

3.4. Lab Visit Measures

We will assess several baseline measures to characterize the study samples.

3.4.1. Self-Report Measures

The participants will complete online self-report surveys via REDCap. Study staff will register participants in REDCap and provide a participant-specific URL to access the surveys. The survey battery will take approximately 20 minutes and study staff will be available to assist as needed. See above table for measures and participant demographics and clinical characteristics: demographic questions (age, sex, gender, race, ethnicity, education, income, marital status,

employment status & healthcare coverage), clinical survey (e.g., time since diagnosis, MS subtype, brief medical and psychiatric history, and other clinical characteristics), and treatment survey (e.g., medications and therapies).

Ambulatory measures

Motor Function: We will administer a 4-m backward walking test, evaluation of gait speed (4 meter walk test), and gait endurance (2-minute walk test).

Backward gait speed: Backward walking is used to assess balance and fall risk. Participants walk backwards a short distance at their usual pace, completing one practice and two-timed trials. Scores are recorded as time in seconds required to walk 4 meters on each of two trials, with the better trial used for scoring. The test time is ~3 minutes.

Gait speed: The 4-meter walking test measures locomotion. Participants walk a short distance at their usual pace, completing one practice and two-timed trials. Scores are recorded as time in seconds required to walk 4 meters on each of two trials, with the better trial used for scoring. The test time is ~3 minutes.

Gait endurance (2-minute walk test): This test assesses the ability to sustain effort that requires conjoint work capacities from cardiopulmonary function, biomechanical, and neuromuscular function. The test time is ~4 minutes.

4. Data Management: Storage and Sharing

We will use REDCap to collect and store study data and participant identifiers. We will (1) assign each participant an ID number in REDCap to maintain confidentiality and (2) use this ID number to code/label study data. The link between the study data and a participant's identity will only exist in REDCap, to which only research staff members have access.

We will label any paper forms only with the ID number and keep them in a locked cabinet separate from any identifying information and will scan and upload them to REDCap as a source document.

We will track protocol deviations and adverse events in REDCap.

5. Data Analysis/Statistical Methods

5.1. Sample Size Determination

The study sample size ($N = 20$) is consistent with pilot studies that seek to examine feasibility, usability, and satisfaction of an intervention or device, and provides an opportunity to collect preliminary data on efficacy. Consistent with pilot studies in general, this sample size is underpowered to make definitive conclusions about the effect of the device on primary outcomes; in contrast, it is sufficient for serving as the basis for future applications for full-size trials that are sufficiently powered to test such outcomes.

5.2. Analysis of Study Aims

To describe the sample, we will report the number of participants approached (and recruitment

source), eligible, excluded, declined, enrolled, randomized, and who provided data at each assessment point (including reasons for exclusion and declination). Before conducting the primary analyses, we will examine distributions of all variables for outlying values and skewness; where indicated, we will recode or transform variables. For aim 1, we will calculate descriptive and frequency analyses. For aim 2, we will conduct analyses to assess for statistically significant within-person change on the target outcomes (activity (primary outcome), physical function, and quality of life, and decreasing physical and psychological symptom (e.g., pain, fatigue, depression) severity).

6. Human Subjects Protections

6.1. Potential risks

The risks associated with the proposed study are minor and infrequent.

Confidentiality is a concern in this study. We will make every effort to keep the research information in the strictest confidence, but we cannot guarantee that accidental disclosure will not happen. We remind participants that the responsibility of confidentiality rests with everyone: they should think carefully before discussing their role in this study with anyone since the effects of disclosure are unknown.

Participants may experience fatigue and/or boredom while completing the assessments, exercise sessions, and logs. Some participants may experience mild muscle soreness from the exercise and may also experience mild anxiety, frustration, and/or stress while answering questions about exercise and mood.

6.2. Adequacy of Protection Against Risk

6.2.1 Informed Consent

The UW IRB approved the protocol for this study. Research staff members will ask interested people a set of formalized questions to determine eligibility based on the inclusion/exclusion criteria. They will obtain non-written consent to ask potential participants eligibility questions before initiating the screening process. Individuals who are interested in participating will be allowed to ask any questions about the study and their participation, and if they opt to enroll, they will provide written informed consent before completing any study assessments; a copy of their signed informed consent document will be provided to the participant.

6.2.2. Protection against Risks

To minimize the potential for risks, we will brief participants in detail as to what they will experience throughout the study. We will inform all participants that they may terminate participation in the study at any time without penalty.

To reduce the risk to confidentiality, we will

1. assign each participant an ID number to maintain confidentiality
 - a. use this ID number to code/label study data
 - b. keep this link between the study data and a participant's identity in the form of the unique study code that will only exist in REDCap, to which only research staff members have access. REDCap is a secure, web-/cloud-based system approved for research use, with access limited to the study team.

2. use REDCap to collect and store study data and participant identifiers.
3. label any paper forms only with the ID number and keep them in a locked cabinet (in which only research staff will have keys) separate from any identifying information and will scan and upload them to REDCap as a source document.

Throughout the consent process and study, we will inform participants that they do not have to discuss any topics they do not wish to. In addition, we will inform participants during the consent process that they are free to stop any session or assessment at any time. Participants may refuse to answer any questions that make them feel uncomfortable.

We will inform all participants of their right to withdraw from the study at any point without adversely impacting their routine medical, psychiatric, or psychotherapeutic care.

If participants experience fatigue or frustration during lab-visit assessments, we will encourage them to take a break, and remind them that they do not have to answer any questions they do not wish to answer and that they may terminate participation in the study at any time without penalty.

We will instruct the participant to contact the study team if they experience any negative experiences from using the Cubii unit. Study team members will attempt to troubleshoot issues related to discomfort with using the unit, such as ensuring the foot straps are not too tight and good posture while seated. We will minimize this risk by telling the participants that it may take a few days to get used to using the Cubii.

Although the study poses no serious risks to participants, participants may notify research personnel about pre-existing mental health issues that have not been previously identified. Staff will implement a suicide risk assessment protocol (see document “Suicide Protocol”). Some participants may have difficulty moving the 29lbs unit from and into their vehicle. We will screen participants to ensure they can, or someone can assist them to, move the unit without risk.

7. Monitoring Plan and Information

All research personnel involved in any way in this project will have completed training in the protection of human research participants per guidelines issued by the U.S. Department of Health and Human Services, Office for Human Research Protection. The IRB and other necessary regulatory and oversight entities will review and approve this protocol before implementation.

The principal investigator will check with staff weekly to discuss study activities, progress, and troubleshoot any issues including recruitment efforts, data collection (including data management and clearing of queries), and discussion of any protocol deviations or adverse events. Additionally, ongoing training will occur as needed.

8. Importance of Knowledge to be Gained

The findings from this study can advance implementation of rehabilitation strategies to restore function, reverse symptoms, and enhance quality of life for people with MS.

9. Study Discontinuance and Closure

In the event a participant withdraws from the study or is lost to follow-up, staff will make all attempts to exit the participant in accordance with the protocol requirements and record the reason for discontinuation.

